Statistical Analysis Plan for the study: "The effects of Menaquinone-7 supplementation in patients with severe coronary calcifications: study protocol for a randomized controlled trial"

SAP authors: [name] ^a, [name] ^b, [name] ^a

Affiliations:

^a Open Patient data Explorative Network (OPEN), Odense University Hospital and Department of Clinical Research, University of Southern Denmark, Odense, Denmark

^b Department of Cardiology, Odense University Hospital, Odense, Denmark

Introduction

This document specifies the planned statistical analysis for the study "The effects of Menaquinone-7 supplementation in patients with severe coronary calcifications: study protocol for a randomized controlled trial" as carried out following the protocol published at ClinicalTrials.gov Identifier: NCT05500443.

Sample size considerations

According to the protocol (1): "We are planning a study of a continuous response variable from independent control and experimental subjects with 1 control per experimental subject. In the AVADEC trial, the mean (standard deviation) two-year CAC progression among 182 men with CAC score ≥ 400 was 380 AU (330 AU) in the placebo group and 288 AU (280 AU) in the intervention group. The joint standard deviation was 311 AU. If this is true in a population of men and women, inclusion of 180 experimental subjects and 180 control subjects are needed to be able to reject the null hypothesis that the population means of the experimental and control groups are equal with probability (power) 0.8. The Type I error probability associated with this test of this null hypothesis is 0.05 (two-sided). Accordingly, 360 subjects are needed. However, to comply with the uncertainty and to account for drop-out of 10%, 400 patients will be included. The sample size is based on two years of treatment."

Randomizations

Randomization is performed by the pharmacy at Odense University Hospital. Based on a computergenerated assignment scheme the tablets will have a random number according to the sequential order.

Statistical principles

All analyses were performed in the intention-to-treat population and as superiority analyses. Two-sided p-values of 0.05 or less were considered to indicate statistical significance and associations and effect estimates will be reported with 95% probability symmetric confidence interval (2.5% to 97.5% quantile).

Practical considerations

Data are collected using REDCap hosted by OPEN (Open Patient data Explorative Network, Odense University Hospital, Odense Denmark) with project number OP_1703. Data are analyzed using Stata on OPEN's secure analysis server (OPEN Analyse). A prespecified random seed of 319846 will be used for bootstrapping and/or imputation if these methods are deemed nescessary.

Planned analyses for primary publication

Outcomes

Primary outcome: Main analysis

The primary outcome is the change in coronary artery calcification (CAC) score (numerical) from baseline to 24 month for the full cohort of included patients.

Secondary outcomes

Secondary outcomes are:

- Change in CAC score from baseline to 24 months in men and women, respectively
- Change in CAC score from baseline to 24 months in two pre-specified subgroups (baseline CAC score <1000 and ≥ 1000)
- Change in coronary plaque composition by contrast CT from baseline to 24 months
- Change in calcifications in the aortic valve by non-contrast CT from baseline to 24 months
- Cardiac events (non-fatal myocardial infarction, coronary revascularization, and cardiac death) during the follow-up period
- Change in quality of life from baseline to 24 months.

An exploratory endpoint is:

• Change in MGP with different phosphorylation (p and dp) and carboxylation forms (c and uc).

Safety outcomes

Safety outcomes are:

- Death
- Cardiovascular events (myocardial infarction, coronary revascularization, heart valve surgery, stroke, significant aortic disease (dissection, rupture and surgery) and significant peripheral artery disease (thromboembolisms and surgery)
- Venous thromboembolism including pulmonary embolism
- Bleeding (including intracranial bleeding and hemorrhage associated with a drop in hemoglobin of
 ≥ 2mmol/I)
- Cancer, including solid and hematologic
- Significant deterioration in laboratory measurements (hemoglobin, creatinine (eGFR), sodium, potassium, calcium, magnesium, albumin, phosphate, alkaline phosphatase, parathyroid hormone or prothrombin time-international normalized ratio (PT-INR)).

Dichotomous safety outcomes are evaluated as occurred / not occurred between baseline and 24 months. Numerical safety outcomes are evaluated as change from baseline to 12 and 24 months.

Planned tables and figures and corresponding analyses

Table 1. Characteristics of patients at baseline

Characteristics (as listed in Table 1 below, numerical characteristics marked with [numerical]) of patients at baseline will be reported separately for the two treatment groups. Characteristics will be reported as

Mean and standard deviation (SD) for numerical characteristics, which are approximately normally distributed in both treatment groups as investigated by normal quantile-quantile plots.

Median and 1st and 3rd quartile (inter quartile range (IQR)) for numerical characteristics, which are not approximately normally distributed in at least one treatment group as indicated by normal quantilequantile plots.

Counts and proportions for categorical characteristics (with categories as specified in Table 1 below).

As the intervention is randomized, no differences between groups will be estimated. Number of missing observations in each group will be specified.

Characteristics	Vitamin K +D group (N=XX)	Placebo group (N=XX)
Age – years [numerical]		
Body-mass index – kg/m ² [numerical]		
Coexisting condition – no (%)		
Diabetes		
Hyperlipidemia		
Hypertension		
• Renal failure, eGFR < 60 mL/min1.73 m ²		
Family history of premature CVD - no (%)		
Smoking status - no (%)		
Active smokers		
Former smokers		
Non-smokers		
Total cholesterol – mmol/L [numerical]		
HDL – mmol/L [numerical]		
LDL – mmol/L [numerical]		
Estimated GFR – ml/min/1.73 m ² [numerical]		
dp-ucMGP – pmol/L [numerical]		
Systolic blood pressure – mmHg [numerical]		
Diastolic blood pressure – mmHg [numerical]		
Medications – no (%)		
ACE inhibitor or ARB		
Beta-blocker		
 Mineralocorticoid-receptor antagonist 		
Antiplatelet therapy		
• NOAC		
Statin therapy		
Baseline CAC score – AU [numerical]		
• 400-999 AU - no (%)		

٠	≥ 1000 AU - no (%)				

ACE denotes angiotensin-converting enzyme, ARB angiotensin-receptor blocker, CAC coronary artery calcification, dp-ucMGP dephosphorylated-uncarboxylated Matrix Gla-Protein, GFR glomerular filtration rate, HDL high-density lipoprotein, LDL low-density lipoprotein, NOAC new-onset anticoagulant

Table 2. Primary outcome and numerical secondary outcomes

Primary outcome and numerical secondary outcomes will be analyzed by mixed effects linear regression. The mixed effects linear regression models will include a fixed effect for treatment, a fixed effect for time point (baseline, 12 and 24 months) and a fixed effects interaction between treatment and time point. As baseline measurements are obtained before randomization, treatment at baseline will be modelled as a separate common treatment category, constraining baseline measurements to no systematic treatment effect between the two treatment arms, as suggested in literature (6). All mixed effects models will include a random intercept for each included patient. Normality assumptions on residuals and random effects will be evaluated by normal quantile-quantile plots. In case deviations from normality assumptions are detected analyses will be repeated with nonparametric bootstrapping with 1,000 bootstrapping samples (handling individual patients as bootstrapping clusters, and treatment groups as bootstrapping strata).

	Vitamin K+D group	Placebo group	Group difference	
	Mean change from	Mean change	Treatment effect	p-value
	baseline (95 % CI)	from baseline	(95 % CI)	
		(95 % CI)		
Primary outcome				
CAC score (all				
patients)				
Numerical secondary of	utcomes			
CAC score (men)				
CAC score (women)				
CAC score				
(baseline CAC score				
400-999)				
CAC score				
(baseline CAC score				
≥1000)				
AVC score (all				
patients)				
dp-ucMGP				
Quality of life				

All available data will be used in the analyses in Table 2.

Table 3. Secondary outcome on plaque composition

Analyses on change from baseline to 24 months on per patient level in all participants will be carried out similar to Table 2.

	Vitamin K+D group	Placebo group	Group difference	
	Mean change from	Mean change	Treatment effect (95	p-value
	baseline (95 % CI)	from baseline (95	% CI)	
		% CI)		
Plaque volume and c	composition			
Total plaque (mm ³)				
Calcified plaque				
(mm ³)				
Noncalcified plaque				
(mm ³)				
Low-attenuation				
noncalcified plaque				
(<30 HU) (mm³)				

Table 4. Dichotomous secondary outcome and adverse events

Dichotomous secondary outcomes and adverse events are reported as counts and proportions separately for each treatment group and compared between groups by χ^2 -test if all counts are at least 5, or with Fisher's exact test otherwise. If a patient reported multiple events of the same outcomes, this will be handled dichotomously as experiencing the outcome in the analyses, but the count of such patients will be reported in a parenthesis or footnote to the table.

All available data will be used in the analyses in Table 2, and number of missing observations in each group will be specified.

Event	Vitamin K +D group (N=XX)	Placebo group (N=XX)	p-value
Secondary outcome			
Cardiovascular events (combined) – no (%)			
 Non-fatal myocardial infarction 			
Coronary revascularization			
Cardiac death			
Adverse Events			
Any event – no (%)			
Death – no (%)			
Cardiovascular events (combined) – no (%)			
Myocardial infarction			
Coronary revascularization			
Heart valve surgery			
• Stroke			
 Significant aortic disease (dissection, rupture and surgery) 			
Significant peripheral artery disease			
(thromboembolism and surgery)			
Venous thromboembolism – no (%)			
Severe bleeding – no (%)			
Incident cancer – no (%)			

Table 5. Numerical safety outcomes

Numerical safety outcomes will be analyzed by linear mixed models corresponding to the analyses specified for the primary outcome in Table 2. No subgroup analyses will be performed.

	Vitamin K+D group	Placebo group	Group difference	
	Mean change (95 %	Mean change	Treatment	P-
	CI)	(95 % CI)	effect (95 % CI)	value
hemoglobin				
creatinine (eGFR)				
carbamide				
sodium				
potassium				
calcium				
magnesium				
albumin				
phosphate				
Alkaline phosphotase				
parathyroid hormone				
prothrombin time-				
international				
normalised ratio (PT-				
INR)				

Supplementary Table S1. Stratified analyses of the primary outcome

Analyses of the primary outcome (progression in CAC score) will be repeated stratifying for age (below or above mean age at baseline), diabetes (yes / no at baseline), hypertension (yes / no at baseline), renal failure (yes / no at baseline), statin therapy (yes / no at baseline), and MGP (below / above median). In these analyses, patients will not be stratified by baseline CAC score 400-999 and ≥1000. The same models as for Table 2 will be applied for these analyses.

	Vitamin K +D group	Placebo group		
	Mean change from baseline (95 % CI)	Mean change from baseline (95 % CI)	Treatment effect (95 % CI)	P-value
Below mean age				
Above mean age				
No diabetes				
Diabetes				
No hypertension				
Hypertension				
No statin therapy				
Statin therapy				
No renal failure				
Renal failure				
Baseline MGP <				
median				
Baseline MGP >= median				

Supplementary Table S2. Sensitivity analysis: Primary outcome and numerical secondary outcomes with imputation

If more than 5% of observations are missing at 24 months for the main analysis of the primary outcome reported in Table 2 the analysis will be repeated using multiple imputation (assuming missing at random) by mixed effects linear regression with all baseline characteristics included in Table 1 as covariates generating 100 imputations. Results will be reported in a table structured as Table 2.

	Vitamin K+D group	Placebo group			
	Mean change from	Mean change from	Treatment effect	p-value	
	baseline (95% CI)	baseline (95% CI)	(95% CI)		
Primary outcome: N	Primary outcome: Main analysis with imputation				
CAC score (all					
patients)					

Supplementary Table S3. Reasons of abandoning the study

	Vitamin K+D group (n=)	Placebo group (n=)
Excluded after inclusion		
Withdraw informed consent		
Significant comorbidity		
Lost interest		
Experienced side effect		
Personal reasons		
Died		

Figure 1. Enrollment and Randomization of Patients

[figure not shown]

Figure 2. CAC progression according to treatment allocation

CAC score at baseline, 12, and, 24 months will be presented in a graph, where the two treatment groups are plotted with their means and 95% confidence intervals (as obtained from the linear mixed models applied for Table 2). The figure will be presented for all patients (Figure 2A) as well as stratified by the baseline CAC score subgroups 400-999 (Figure 2B) and ≥1000 (Figure 2C). (See mockup figure 2A below, 2B and 2C are similar)

[figure not shown]

Figure 3. Change in plaque volume from baseline to 24 months

Change in plaque volume (mm³) with the 4 groups (total, calcified, noncalcified, low-attenuation noncalcified plaque) from baseline to 24 months follow-up will be presented as a box plot to show difference between the treatment group and placebo group.

[figure not shown]

Figure 4. Forest plot of stratified analyses of the primary outcome

Coefficients with 95% confidence intervals from stratified analyses (as reported in Supplementary table 1) for differences in primary outcome (change of CAC score from baseline to 24 months) between treatment groups will be presented as a forest plot. (See mockup figure below.)

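### The 0.05 significance rule is not confined to the primary test, so a trial with no effect has about a 12% chance of a 'significant' CAC result in a Table 2 subgroup while the primary test is not significant

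*SAP*

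**What the plan says.** The SAP names one primary outcome: CAC change from baseline to 24 months in the full cohort. 'Sample size considerations' attaches the error rate to that single comparison: "The Type I error probability associated with this test of this null hypothesis is 0.05 (two-sided".

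'Statistical principles' then gives the decision rule: "Two-sided p-values of 0.05 or less were considered to indicate statistical significance". The sentence has no qualifier. The preceding sentence speaks of all analyses, but that phrase governs the intention-to-treat population and the superiority framing. The p-value rule is simply unrestricted.

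The list under 'Secondary outcomes' includes "Change in CAC score from baseline to 24 months in men and women, respectively", followed by the same change in the two baseline CAC strata. Table 2 gives each of these four its own row with a treatment effect and a p-value. For Supplementary Table S1, "Analyses of the primary outcome (progression in CAC score) will be repeated stratifying for age" and five further factors, which gives 12 more within-stratum rows with p-values.

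The SAP states no testing order, gatekeeping rule, multiplicity adjustment or treatment-by-subgroup interaction test. It does not say that p-values beyond the primary one are descriptive.

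**The concern.** The same endpoint is tested five times in Table 2, and four of those tests are ranked as secondary outcomes rather than as exploratory subgroup checks. With no interaction test planned, the only inferential statement about a subgroup is its own p-value, read against 0.05. A trial with a neutral primary result could therefore report a statistically significant CAC effect in one sex or one CAC stratum and be following its own prespecified rule. What is at stake is what the trial may claim when the full-cohort test fails, not the validity of the full-cohort test.

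**Working it through.** **1. The SAP's own figure.** Inputs from 'Sample size considerations':
- means and SDs: "was 380 AU (330 AU) in the placebo group and 288 AU (280 AU) in the intervention group", a difference of 380 − 288 = 92 AU
- "The joint standard deviation was 311 AU"
- allocation "with 1 control per experimental subject"
- two-sided alpha 0.05
- the means "are equal with probability (power) 0.8", that is, 80% power

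n per arm = 2 × (1.960 + 0.842)² × 311² / 92² = 179.4, rounded up to 180. Then 360 / 0.90 = 400. Both match the SAP. Power at 180 per arm is 0.801 (normal approximation) or 0.799 (noncentral t). The calculation uses alpha = 0.05 for one test only.

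**2. Overlap of the five CAC tests.** Let p_m be the share of men and p_l the share with baseline CAC below 1000. The SAP gives neither, so both are varied. Sex and stratum are taken as independent, which makes four cells with weights p_m·p_l, p_m(1 − p_l), (1 − p_m)p_l and (1 − p_m)(1 − p_l). Under no effect, each cell contributes an independent normal term with variance w·s² (w the cell weight, s the cell SD). Each test statistic is the sum over its cells divided by the square root of the summed variances. With equal SDs this implies:
- corr(all, men) = √p_m
- corr(all, below 1000) = √p_l
- corr(men, below 1000) = √(p_m·p_l)
- corr(men, women) = 0, and likewise for the two CAC strata

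For example, p_m = 0.75 and p_l = 0.5 give 0.87, 0.71 and 0.61 for the first three.

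**3. Error rates under no effect.** Two-sided 0.05 for each test, equal SDs, 1,000,000 draws per scenario:

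| p_m | p_l | Any of the 5 | Any of the 4 subgroups | Subgroup significant, primary not |
|---|---|---|---|---|
| 0.50 | 0.50 | 16.9% | 16.1% | 11.9% |
| 0.70 | 0.50 | 16.8% | 16.0% | 11.8% |
| 0.75 | 0.50 | 16.8% | 16.1% | 11.8% |
| 0.90 | 0.40 | 16.5% | 16.0% | 11.5% |
| 0.90 | 0.60 | 16.5% | 16.0% | 11.5% |

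Over 50-90% men and 40-60% below 1000, the last column runs from 11.5% to 11.9%. It equals the first rate minus the primary test's 5%, for example 16.8% − 5% = 11.8%. Widening p_l to 30-70% gives 16.4-16.9% for any of the five.

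**4. Sensitivity to unequal SDs.** If the SD in the stratum at or above 1000 is 1.5 to 3 times larger, the rate for any of the five is 15.8-16.9%. Subtracting 5% leaves 10.8-11.9% for a subgroup result without a primary result.

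**5. Reference points.** Treating the five tests as independent would give 1 − 0.95⁵ = 22.6%, which overstates the rate because the tests share patients. The chance that any of the five is falsely significant in one given direction, such as benefit, is about 8.5%.

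**6. Table S1.** Six factors with two strata each add 12 tests of the same endpoint. They lie outside the figures above and can only raise them. No figure is given here, because it depends on the prevalence of each factor.

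**The case against.** The best defence is that the trial has one primary outcome, one time point and one population, and that everything else is labelled secondary, exploratory or safety. Leaving secondary outcomes unadjusted is common in such a design, and they are normally read as supportive. The SAP never says that a secondary result can establish efficacy or rescue a failed primary. It is right that the primary type I error is intact and that adjustment is not obligatory. But the labels do not limit where the significance rule applies, and nothing in the SAP tells the reader to take the other p-values as nominal.

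A reader might infer a much larger problem from the number of planned p-values. The shells hold 8 + 4 + 16 + 12 + 12 + 1 = 53 (Tables 2, 3, 4, 5, S1, S2), which at 0.05 for each of the 52 non-primary tests suggests 52 × 0.05 = 2.6 chance findings. The document does not support that reading:
- Twenty-four of the rows are adverse events or laboratory safety measures, where multiplicity control is not normally expected.
- S2 is conditional on more than 5% missing data and repeats the primary hypothesis.
- Three Table 4 rows are components of the cardiac composite.
- The chi-square/Fisher rule in Table 4 is conservative for rare events. With 200 per arm its actual size is 0.5%, 1.7%, 2.3% and 4.1% at assumed event rates of 1%, 2%, 3% and 5%.

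A reader might also take the 11 tests that carry the listed secondary outcomes and compute 1 − 0.95¹¹ = 43%. That assumes independence, yet the CAC subgroups share patients and total plaque contains its calcified and noncalcified parts. It is at most an upper reference.

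**Conclusion.** The point holds for the CAC subgroup tests. Under no effect, following the stated rule gives about a 12% chance of declaring a significant CAC effect in at least one Table 2 subgroup while the primary is not significant, and about 16-17% for any of the five CAC tests. The 12% is the figure that matches the harm, because the 16-17% includes the 5% already accepted for the primary test. The results assume no effect in any subgroup, sex independent of CAC stratum, 50-90% men and 40-60% with baseline CAC below 1000. They change little over those shares and fall by at most about one percentage point when SDs differ between strata.

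Two stronger conclusions do not follow. The 5% error rate of the primary test is not inflated. And the SAP is not without any ranking of outcomes: what it lacks is a testing order, or a statement of how p-values beyond the primary are to be read. The change is worth making because it alters what the trial may conclude from a neutral primary result.

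**What to change.** In 'Statistical principles', state that the two-sided 0.05 rule applies only to the primary test (24-month CAC change, all patients). State also that secondary, subgroup and Table S1 results are supportive and are reported as estimates with 95% confidence intervals, with any p-value labelled nominal and unadjusted for multiplicity. If the sponsor wants confirmatory secondary claims, test the listed secondary outcomes with Holm's procedure, and only after a significant primary result.

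Under no effect, either option holds the chance of a declared CAC effect across the five Table 2 tests at 5%. The safety tables need no change.

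The cost is a few lines of text, with no new data and no loss of power for the primary test. The downside is that secondary and subgroup results lose the label of statistical significance, or can gain it only after a positive primary result.

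### The random-intercept-only covariance ties the baseline adjustment of the 24-month CAC contrast to a slope below 1 and gives up precision if progression rises with baseline CAC

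*SAP*

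**What the plan says.** Under the heading for Table 2, the SAP analyses the primary outcome with a linear mixed model on CAC at baseline, 12 and 24 months. The fixed effects are treatment, time point and their interaction. Baseline is handled as a common category, "constraining baseline measurements to no systematic treatment effect between the two treatment arms". The only covariance feature named is a random intercept per patient; no random slope, residual structure or unstructured covariance is given. Tables 3 and 5 and Supplementary Table S1 use the same approach. If normality fails, the analysis is repeated with a patient-level bootstrap. The Table 1 characteristics enter only the imputation analysis in Supplementary Table S2.

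The sample size section rests on something simpler, a two-group comparison of mean two-year change. Progression in an earlier trial in men with CAC of at least 400 "was 380 AU (330 AU) in the placebo group and 288 AU (280 AU) in the intervention group", and "The joint standard deviation was 311 AU". From this the SAP concludes that "inclusion of 180 experimental subjects and 180 control subjects are needed" to reject the hypothesis that the means "are equal with probability (power) 0.8".

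Baseline CAC is also used to define a secondary analysis: "Change in CAC score from baseline to 24 months in two pre-specified subgroups (baseline CAC score <1000 and ≥ 1000").

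**The concern.** A random intercept alone makes every pair of visits equally correlated and every visit equally variable (compound symmetry). Together with the common baseline mean, this fixes how far the 24-month contrast is adjusted for a chance difference in baseline CAC: the slope equals the ICC, which cannot reach 1. A change score uses slope 1. If progression rises with baseline CAC, the best slope is above 1, so the planned model sits further from the optimum than the change score on which the sample size was built. Randomisation keeps the estimate unbiased. What is at stake is its precision, and how much of the information in a baseline scan that every patient has is actually used.

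**Working it through.** **Inputs from the SAP.** Difference 380 − 288 = 92 AU; SD of change 311 AU; two-sided alpha 0.05; power 0.80; allocation 1:1; 180 per arm; 10% dropout.

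**Inputs not in the SAP (assumed).** Baseline SD (SD0) 500 to 1500 AU; correlation r between baseline CAC and 24-month change, 0 to 0.5. Two patterns over time: (a) linear, where the 12-month change is half the 24-month change; (b) accumulating, where half the baseline-related change has occurred by 12 months and the rest of the change builds up in two independent, equal steps.

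**Step 1. The SAP's own figure.** n per arm = 2 × [(1.960 + 0.842) × 311 / 92]² = 179.4, so 180. The SE of the difference is 311 × √(2/180) = 32.8 AU, and power is 0.801 by the normal formula (0.799 by the noncentral t). 360 / 0.9 = 400. The figure reproduces.

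**Step 2. The planned estimator.** With complete data, the treatment effect at 24 months is

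diff(Y24) − ICC × diff(Y0).

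Writing Y24 = Y0 + C, with C the change, its variance per patient is

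311² + [(1 − ICC) × SD0]² + 2 × (1 − ICC) × SD0 × r × 311.

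This exceeds 311² whenever r ≥ 0. The best slope is 1 + r × 311 / SD0, and a freely estimated slope leaves variance 311² × (1 − r²).

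**Step 3. The ICC that the model would fit.** This is the mean between-visit covariance divided by the mean variance. Worked case, pattern (b), SD0 = 500, r = 0.5:

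- Variances at 0, 12 and 24 months: 250,000; 370,066; 502,221. Sum 1,122,287.
- Covariances 0–12, 0–24 and 12–24: 288,875; 327,750; 414,986. Sum 1,031,611.
- ICC = 1,031,611 / 1,122,287 = 0.919. Best slope = 1 + 0.5 × 311 / 500 = 1.311.
- (1 − ICC) × SD0 = 0.0808 × 500 = 40.4. Variance = 96,721 + 1,632 + 12,564 = 110,917, so SD 333.0 and SE 35.1 AU, 7.1% above 32.8.
- Power = Φ(92/35.1 − 1.96) = 0.746 (noncentral t 0.743).
- Free slope: SD 311 × √0.75 = 269.3, SE 28.4 AU, power 0.90.

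Simulated REML fits of the planned model in this setting (600 trials each with and without an effect) gave an SE 6.9% to 7.3% above the change score, in line with the formula.

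**Step 4. Range over SD0 500 to 1500 and both patterns** (noncentral t, 180 complete patients per arm, correct SE):

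| r | Planned model | Free slope | Variance ratio |
|---|---|---|---|
| 0 | 78.7–79.8% | 79.9% | 1.00–1.03 |
| 0.2 | 76.6–79.1% | 81.5% | 1.07–1.13 |
| 0.35 | 75.3–78.5% | 84.8% | 1.18–1.28 |
| 0.5 | 74.3–78.0% | 89.8% | 1.40–1.53 |

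For r of 0.2 to 0.5 the planned SE is 1.01 to 1.07 times the change-score SE. In patients per arm for 80% power, that is 184 to 206 for the planned model. With a free slope, 179.4 × (1 − r²) gives 173 at r = 0.2 and 135 at r = 0.5.

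**Step 5. Dropouts with a 12-month scan.** The planned model uses them; a completers' t-test does not. If 10 to 20 dropouts per arm contribute 12-month data, the SE relative to a t-test on 180 completers per arm falls to about 0.99 to 1.06. In the milder cases this removes the loss.

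**The case against.** Several points on the other side stand.

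- **The common baseline mean is not the fault, nor is the lack of a baseline covariate.** A reader might infer either from the model description. But a constrained baseline is itself a baseline adjustment; with an unstructured covariance the same model would adjust about as well as ANCOVA. The cause is the covariance.
- **The adjustment does not go the wrong way.** It removes most of the imbalance: at r = 0.35 and SD0 = 500 under the accumulating pattern, 0.911 of the 1.218 needed, or 75%. It moves away from the optimum only relative to a change score.
- **The SAP does not show that progression rises with baseline CAC.** The split at 1000 AU shows interest in subgroups; it gives neither the sign nor the size of a correlation.
- **The sample size is not shown to be wrong.** The shortfall against 80% is 0 to 6 points. The larger gaps compare the plan with a better model, not with its own calculation.
- **The powers above assume a correct SE.** If changes accumulate over time, the model-based SE is only 0.66 to 0.80 of the true one for r of 0.2 to 0.5. The planned test would then reject about 88–92% of the time at 92 AU, but with type I error of about 12–20%. That is not real power, and the reported interval would not reveal the lost precision.

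Two defences do not hold. The bootstrap is triggered only by non-normality and refits the same model, so it can repair the SE but not the estimate. And although the SAP does not say that the random intercept is the sole covariance term, it names no other, so the model as written is compound-symmetric.

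**Conclusion.** The point holds as a conditional loss of efficiency caused by the covariance structure. The planned slope is below 1 whatever the data show. If r is positive, the estimate is slightly less precise than the change score behind the sample size, and clearly less precise than one with a free baseline slope: about 2 to 5 power points at r = 0.2, 6 to 10 at 0.35 and 12 to 16 at 0.5. At r = 0 the cost is about one point or less. These sizes rest on the assumed r, baseline SD and time patterns, none of which the SAP gives, and on complete data. The documents do not support reading this as bias or as a failed sample size calculation. It is worth changing because a free slope needs no assumption about r and costs almost nothing.

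**What to change.** Before database lock, keep the constrained-baseline model and the use of all available data, but replace the random-intercept-only covariance with an unstructured 3 × 3 covariance over baseline, 12 and 24 months. The data then set the baseline slope. Equivalently, model the 12- and 24-month values with baseline CAC × time and an unstructured residual covariance. That version drops patients with only a baseline scan and the baseline estimate that Figure 2 plots, so the first is the better fit to this SAP.

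Adding baseline CAC × time while keeping the random intercept is not enough: if changes accumulate, the model-based 24-month SE stays at about 0.79 to 0.89 of the true SE.

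Use the same covariance for the other repeated-visit models in Tables 2, 3, 5 and S1. The cost is one paragraph of SAP text and a few more covariance parameters (six in place of two with three visits). Sex and age terms are optional.

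### The random-intercept model can understate the 24-month standard error, and the SAP does not say whether the model-based or the bootstrap result fills Table 2 and decides the primary outcome

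*SAP*

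**What the plan says.** The SAP section on Table 2 analyses CAC at three visits with treatment, visit and their interaction as fixed effects and a common baseline mean for both arms. On covariance it says only: "All mixed effects models will include a random intercept for each included patient". No random slope, unstructured residual covariance or robust SE is named.

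On checking, "Normality assumptions on residuals and random effects will be evaluated by normal quantile-quantile plots". On the remedy, "In case deviations from normality assumptions are detected analyses will be repeated with nonparametric bootstrapping", with 1,000 samples, patients as clusters and arms as strata. The section on practical considerations leaves use of the bootstrap to a judgement of need.

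The Table 2 shell has one treatment effect with its interval and one p-value per outcome.

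The imputation analysis in Supplementary Table S2 is also described as a repeat. It is titled a sensitivity analysis and has its own table: "Results will be reported in a table structured as Table 2". The bootstrap has neither a label nor a table.

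The same model is reused elsewhere. For Supplementary Table S1, "The same models as for Table 2 will be applied for these analyses". Figure 2 takes its means and intervals "as obtained from the linear mixed models applied for Table 2", and is also shown "stratified by the baseline CAC score subgroups 400-999" and 1000 AU or more.

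**The concern.** A random intercept alone implies compound symmetry, so the change between any two visits has the same variance. If patients progress at different rates, the 24-month change varies more than the 12-month change. The model then averages the smaller variances into the one it uses for the 24-month contrast, and that SE comes out too small.

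The bootstrap resamples whole patients, so it gives a sound SE whatever the covariance. Two weaknesses remain. It is switched on by a check of normality, although the fault lies in the covariance. And when it is switched on, two intervals and two p-values exist for the primary outcome, Table 2 has room for one of each, and no rule picks between them. The choice could be made after both are seen.

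**Working it through.** **Inputs from the SAP (sample size section).** Means of 380 and 288 AU, so a planned difference of 92 AU; for the SD, "The joint standard deviation was 311 AU"; 180 per arm; two-sided 5%; power 80%. Subgroup labels start at a CAC score of 400 AU.

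**Inputs assumed.** The 12-month SD, the baseline SD and shape, and the scan error. The SAP gives none of these.

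**The plan's own figure.** n per arm = 2 × (1.960 + 0.842)² × 311² / 92² = 179.4, so 180. This reproduces. The simple SE of the 24-month difference in change is 311 × √(2/180) = 32.8 AU.

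**Short formula.** The random-intercept model estimates one change variance, roughly the mean of the three:

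ratio of model SE to true SE ≈ √[(v(0–12) + v(12–24) + v(0–24)) / (3 × v(0–24))]; type I error = 2 × [1 − Φ(1.96 × ratio)].

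Take a 12-month SD of 220 AU, with the same SD for months 12–24:
- v = 48,400, 48,400 and 96,721; mean 64,507; square root 254.0
- ratio 254.0/311 = 0.817
- type I error = 2 × [1 − Φ(1.601)] = 10.9%.

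**Full model.** The short formula ignores the growth in the variance of CAC itself between visits. The second column therefore fits the common-baseline random-intercept model at its best-fitting parameters and compares its SE with the true (sandwich) SE. It takes 180 per arm, complete data, baseline SD 626–1000 AU and baseline uncorrelated with later change.

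| 12-month SD (AU) | Type I, short formula | Type I, full model |
|---|---|---|
| 311 | 5.0% | 5.5–6.2% |
| 280 | 6.7% | 7.2–7.9% |
| 240 | 9.4% | 9.9–10.5% |
| 220 | 10.9% | 11.4–12.0% |
| 200 | 12.6% | 13.0–13.6% |
| 156 (half of 311) | 16.5% | 16.9–17.4% |

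At 220 AU the full calculation gives a model SE of 26.3–26.6 AU against a true SE of 32.9–33.1 AU. A positive correlation between baseline level and progression adds to the error: with a 12-month SD of 241 AU and baseline SD of 600 AU, it rises from 9.9% at correlation 0 to 11.9% at 0.6. If the variance of CAC is the same at every visit and all changes vary equally, it is 5.0%.

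**Simulation under no effect.** 10,000 trials per scenario, with baseline either a normal distribution cut at 400 AU or 400 AU plus a gamma variable. With a 12-month SD of 220 AU (random walk), the model-based error was 11.9% and 11.4% for the two baseline shapes; with linear slopes it was 17.2% and 17.4%. Across all scenarios the bootstrap (2,000 trials of 1,000 resamples) had a mean SE of 32.7–33.4 AU and an error of 3.5–6.6%, with Monte Carlo error of about 1 point. Using Shapiro–Wilk p < 0.05 as a stand-in for the Q-Q plot of the random effects, the trigger fired in every run of all 14 scenarios, because baseline CAC is cut off at 400 AU.

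**Can the two results disagree?** With a 12-month SD of 220 AU the significance limits are:
- model: 1.96 × 26.3 = 51.5 AU
- bootstrap: 1.96 × 33.1 = 64.9 AU.

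An observed 58 AU gives z = 58/26.3 = 2.21, p = 0.03 by the model, and z = 58/33.1 = 1.75, p = 0.08 by the bootstrap. The probability that the estimate falls between the limits is 7% under no effect, 15% at a true 46 AU and 10% at the planned 92 AU. With a 12-month SD of about 290 AU (model limit 60.0 AU, bootstrap limit 65.1 AU) these fall to 2%, 5% and 4%.

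**The case against.** The strongest defence is that the bootstrap sits inside the paragraph defining the Table 2 analysis, as the remedy when that model's check fails. Imputation, by contrast, is openly called a sensitivity analysis. On that reading the bootstrap supplies the Table 2 interval and p-value once triggered, and the type I error is about 5%. The general rule on intervals, which refers to the 2.5% and 97.5% quantiles, fits a bootstrap interval but is not tied to one. This reading is plausible, but no sentence states it, and the SAP's other use of a repeated analysis means a check beside the main result.

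The SAP also fixes the trigger, number of resamples, clusters, strata and random seed in advance, and the trigger is the Q-Q plots, not the p-value. That stands. A reader might infer that the analysts will choose after seeing both results. The text supports only that they could.

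A reader might also infer that the bootstrap will fail to trigger and leave the primary test inflated. The calculations point the other way for CAC in all patients, although they use a formal test in place of a visual judgement. The mismatch between trigger and fault is therefore a weakness of design without demonstrated harm to the primary result.

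**Conclusion.** The point holds as a conditional fault in the covariance together with a missing decision rule. The direction is firm: if the spread of CAC change grows with time, the model-based 24-month SE is too small. The size rests on a 12-month SD that the SAP does not give. It runs from about 5.5–6% type I error with no growth in spread of change to about 17% when the 12-month SD is half the 24-month SD.

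These rates apply only if the model-based result is the one reported. It would be wrong to read them as the error of the trial's primary test, because the bootstrap result, if used, holds it near 5%. A bootstrap of the same model leaves the estimate unchanged; only the interval and p-value differ.

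The mechanism plausibly carries to the CAC subgroups, Supplementary Table S1 and Figure 2, but no magnitude was calculated there. Nothing is claimed for the laboratory values in Table 5. The matter should be fixed before the analysis.

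**What to change.** Keep the common-baseline constraint and choose one:

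- **A.** Specify an unstructured 3×3 within-patient covariance (in Stata's mixed command, no random intercept and residuals(unstructured, t(visit))). Keep the bootstrap as a labelled sensitivity analysis. Name a fallback for non-convergence in small subgroups, for example option B.
- **B.** Keep the random intercept and make the patient-cluster bootstrap, or patient-clustered robust SEs, the primary inference whatever the Q-Q plots show.

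With either, add: *The estimate, confidence interval and p-value from this analysis fill Table 2 and decide the primary outcome; any other version is reported as a sensitivity analysis.* Apply the same rule to the CAC subgroups, Supplementary Table S1 and Figure 2.

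The cost is one or two sentences and, for option A, one model option. No new data are needed. Intervals may be wider than the current model-based ones, for example an SE of about 33 AU instead of 26 AU if the 12-month SD is 220 AU.
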